8.4. Duration of Hospital Stay

Time from randomisation to discharge, and time from original admission to discharge, will be summarised overall and by treatment group using median (interquartile range) and compared using Wilcoxon rank sum test. Using this as a continuous outcome variable, the analysis described in section 7.2 will be repeated.

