2.6. Hypotheses and Definition of Primary and Secondary Outcomes

Primary end point

The primary end point of the study is the difference in the proportion of participants with the composite endpoint of death and VAP recurrence rate within 60(± 5) days of enrolment.

Death refers to all-cause mortality. VAP recurrences are episodes which satisfy the US CDC VAP criteria, and verified by two independent respiratory or infectious diseases physicians blinded to the randomisation arm.

The first statistical test for the primary end point will be for non-inferiority. Here, the null hypothesis (H_0): $\theta \geq \delta$ will be tested against the alternative (H_1): $\theta < \delta$, where θ is the treatment effect difference between the proportion of participants who have the primary outcome in the short and long treatment strategy groups, and δ is the fixed non-inferiority margin of 12%.

In the event that short is non-inferior to the long treatment strategy, standard two-sided superiority testing will be performed. That is, the null hypothesis (H_0): $\theta = 0$ will be tested against the alternative (H_1): $\theta > 0$, where θ is the treatment effect difference between the proportion of participants who have the primary outcome in the short and long treatment strategy groups.

Secondary end points

All statistical tests for the secondary endpoints are standard two-sided superiority tests.

a) Ventilator-associated events

Definition: Events which satisfy the US CDC VAP criteria ¹ but were not verified by two independent respiratory or infectious diseases physicians.

H_0 : There is no difference in the proportion of participants who have ventilator-associated events in the short and long treatment strategy groups, i.e. $\theta^{VAE} = 0$;

H_1 : There is a difference in the proportion of participants who have ventilator-associated events in the short and long treatment strategy groups, i.e. $\theta^{VAE} \neq 0$;

where θ^{VAE} is the treatment effect difference between the proportion of participants in the short and long treatment strategy groups.

b) Duration of mechanical ventilation

Definition: Total duration of mechanical ventilation during the 60 days of follow-up after enrolment.

H_0 : There is no difference in the total duration of mechanical ventilation in the short and long treatment strategy groups, i.e. $t^v_s = t^v_l$;

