H_1 : There is a difference in the total duration of mechanical ventilation in the short and long treatment strategy groups, i.e. $t^v_s \neq t^v_l$;

where t^v_s is the duration of mechanical ventilation in the short and t^v_l is the duration of mechanical ventilation in the long treatment strategy groups.

c) Duration of hospitalisation

Definition: Total duration of hospitalisation during the 60 days of follow-up after enrolment.

H_0 : There is no difference in the total duration of hospitalisation in the short and long treatment strategy groups, i.e. $t^h_s = t^h_l$;

H_1 : There is a difference in the total duration of hospitalisation in the short and long treatment strategy groups, i.e. $t^h_s \neq t^h_l$;

where t^h_s is the duration of mechanical ventilation in the short strategy group and t^h_l is the duration of mechanical ventilation in the long treatment strategy group.

d) Acquisition of multidrug resistant infection or colonisation during the hospitalisation

Definition: Growth of multidrug resistant bacteria⁶ from clinically indicated or screening cultures from any source during 60 days of follow-up.

H_0 : There is no difference in the proportion of participants who colonised with multidrug resistant bacteria in the short and long treatment strategy groups, i.e. $\theta^{\text{MDR}} = 0$;

H_1 : There is a difference in the proportion of participants who have ventilator-associated events in the short and long treatment strategy groups, i.e. $\theta^{\text{MDR}} \neq 0$;

where θ^{MDR} is the treatment effect difference between the proportion of participants in the short and long treatment strategy groups.

e) Total number of days of exposure to antibiotics

Definition: Total duration of antibiotic use during the 60 days of follow-up after enrolment.

H_0 : There is no difference in the total duration of antibiotic use in the short and long treatment strategy groups, i.e. $t^a_s = t^a_l$;

H_1 : There is a difference in the total duration of antibiotic use in the short and long treatment strategy groups, i.e. $t^a_s \neq t^a_l$;

where t^a_s is the duration of antibiotic use in the short and t^a_l is the duration of mechanical ventilation in the long treatment strategy groups.

f) Number and types of extrapulmonary infections during hospitalisation (determined from cultures taken from sterile sites)

Definition: Number and types of bloodstream, bone and joint, intracranial, intraabdominal infections during 60 days of follow-up.

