7.2. Statistical Methods Used for Analysis of Primary Outcome

Based on both the ITT and PP population, the proportions of participants experiencing the primary endpoint will be tabulated by treatment group. If the absolute, upper two-sided 90% CIs around the absolute unadjusted difference is less than 12%, then the criteria of non-inferiority will be met.

A multivariable logistic regression model, will be applied on the ITT population to calculate the estimates of the treatment differences adjusted for baseline patient characteristics described above. Categories with low counts may be combined. For example, in the event of comorbidities with very low counts, these comorbidities may be combined to avoid difficulties with the maximum likelihood estimation of the logistic model. Where no

information has been entered on the comorbidities, the participants will be considered not to suffer from these comorbidities.

For the PP population, inverse probability weighting⁹ will be applied to calculate the estimates of the treatment differences using the same baseline patient characteristics as above.

For these multivariate logistic regression models, residual and predicted values produced from the model will be examined to assess the assumptions of the model. Specifically, the assumption of linearity between the predicted log odds and the covariates is assessed by plotting lowess graphs. The independence of the error terms will be considered. Influential cases are investigated by plotting the standardised Pearson's residuals against the predicted probabilities and the leverage of the individual observations.

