8.5. Duration of Mechanical Ventilation

Time from randomisation to extubation, and time from original intubation to extubation, will be summarised overall and by treatment group using median (IQR) and compared using Wilcoxon rank sum test. Using this as a continuous outcome variable, the analysis described in section 7.2 will be repeated.

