8.6. Total Duration of Antibiotics

Total duration of antibiotics from randomisation to 60 days of follow-up will be summarised overall and by treatment group using median (interquartile range) and compared using Wilcoxon rank sum test. Using this as a continuous outcome variable, the analysis described in section 7.2 will be repeated.

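### SAP 8.4 and 8.5 give no rule for participants who die before discharge or extubation, and 8.4 to 8.6 send continuous durations to a binary-outcome analysis

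*SAP*

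**What the plan says.** **Hospital stay.** SAP 2.6 gives "Definition: Total duration of hospitalisation during the 60 days of follow-up after enrolment". SAP 8.4 analyses something different: "Time from randomisation to discharge, and time from original admission to discharge, will be summarised overall and by treatment group", by median and interquartile range with a Wilcoxon rank sum test.

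**Ventilation.** SAP 2.6 gives "Definition: Total duration of mechanical ventilation during the 60 days of follow-up after enrolment". SAP 8.5 analyses "Time from randomisation to extubation, and time from original intubation to extubation", in the same way.

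**Antibiotics.** SAP 8.6: "Total duration of antibiotics from randomisation to 60 days of follow-up will be summarised", again with a Wilcoxon test.

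All three sections then add: "Using this as a continuous outcome variable, the analysis described in section 7.2 will be repeated". Section 7.2 compares an unadjusted difference in proportions with the 12% margin. For the adjusted estimate it states "A multivariable logistic regression model, will be applied on the ITT population", and it adds inverse probability weighting for the per-protocol population.

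Neither document says what duration a participant receives who dies before discharge, before extubation or before day 60. SAP 5.3 reports deaths separately, SAP 7.4 deals with loss and withdrawal, and SAP 7.7 plans no further sensitivity analysis. Protocol 10.1 adds only t tests or Wilcoxon tests for continuous variables.

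**The concern.** Death will be common here. SAP 2.5 cites VAP-attributable mortality of 13.6 to 42.8% and assumes a 55% composite event rate. Protocol section 3 cites all-cause mortality of 20 to 50%. A participant who dies in hospital has no discharge date, and one who dies on the ventilator has no extubation date, so the analysis must do something with them. The possible choices do not agree even on direction.

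Protocol section 4 lists these outcomes under the other clinical benefits of shorter treatment. Protocol 9.2 names higher recurrence and mortality in the short arm as the study's main risk. If that risk materialised, an analysis that ends the count at death would show shorter stay and ventilation in the arm that was doing worse. The choice would also be made late: under SAP 9.2 the trial statistician is not blinded to allocation while preparing and performing the analysis.

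The pointer to section 7.2 is a separate defect. It leaves the adjusted analysis of all three durations undefined.

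**Working it through.** **Three readings of one death.** Take a participant whose stay would have been 28 days and who dies on day 15.
- Death ends the count (the literal reading of SAP 2.6): the score is 15, a short stay.
- No discharge date, so excluded (one reading of SAP 8.4): no score, and the comparison is among those discharged alive.
- Death ranked worst: below every survivor.

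**Inputs from the documents.** 230 per arm (SAP 2.2); two-sided superiority tests for secondary endpoints (SAP 2.6); level 0.05 (SAP 7.3). By chance one named arm is favoured in 0.05/2 = 2.5% of trials. The documents give no figure for the duration endpoints, so there is none to reproduce.

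**Assumptions not in the documents.** Latent stay is the same in both arms: gamma, shape 2, mean 28 days, capped at 60. Time to death is exponential, mean 15 days. There are 2,000 simulated trials per scenario. The Monte Carlo standard error near 20% is √(0.2 × 0.8/2000) = 0.9 points. Ranges below are across separate runs.

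| Mortality, higher v lower arm | Death ends count: higher-mortality arm significantly shorter | Death ranked worst: lower-mortality arm favoured |
|---|---|---|
| 40 v 40% | 2 to 3% | not reported |
| 40 v 35% | about 8% | not reported |
| 30 v 20% | 20% (median about 1.8 days shorter) | not reported |
| 50 v 40% | 19 to 21% | 48 to 51% |
| 52 v 40% | 26 to 28% | 64 to 65% |

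Excluding in-hospital deaths, the higher-mortality arm is favoured in about 5 to 8% of trials at the 10 to 12 point gaps. The distortion is not zero because a longer latent stay leaves more time to die in hospital, so more deaths remove more long stays.

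**Sensitivity to the assumptions.** Raising the mean time to death to 25 days cuts the 52 v 40% figure from 28% to 18%. For 5-point gaps (40 v 35%, 35 v 30%, 45 v 40%), with mean stay 20 to 28 days and mean time to death 15 to 25 days, the rate is 6 to 9% and medians are 0.5 to 1.0 day shorter.

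**Second set of assumptions.** Lognormal stay, median 20 days, log-SD 0.8; death-time scale 7, 15 or 30 days; 600 trials per setting. Rejections here count both directions, so chance is 5%.

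| Mortality | Death ends count: rejection | Median stay, higher-mortality arm |
|---|---|---|
| 35 v 35% | 5 to 6% | no difference |
| 40 v 35% | 7 to 12% | 0.4 to 1.0 day shorter |
| 47 v 35% | 18 to 45% | 1.2 to 2.4 days shorter |

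At the two unequal settings, exclusion gave 4 to 7% rejection and medians 0.2 to 0.7 day shorter. Ranking death worst reversed the sign: medians 0.7 to 14 days longer in the higher-mortality arm.

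**Ventilation and antibiotics.** Ventilation has the same structure as stay and was not simulated separately. For antibiotic days, with the same assumed underlying use in both arms and death ending the count, the higher-mortality arm had a mean 0.3 to 0.5 day lower at 40 v 35% and 0.7 to 1.1 days lower at 47 v 35%.

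**Section 7.2 against 8.4 to 8.6.** A difference in proportions needs a binary outcome, and so does a logistic regression. A duration in days fits neither, and the 12% margin has no meaning on that scale.

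**The case against.** **Direction.** A reader might infer that the plan does score death as a short stay. The documents do not settle this. SAP 2.6 implies it, but time to discharge and time to extubation in SAP 8.4 and 8.5 are undefined for a participant who dies first, and exclusion leaves only a small distortion. This stands: the defect is a missing rule with several open readings, not a chosen wrong rule.

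**Size.** The larger figures need mortality gaps of 10 to 12 points, about the whole non-inferiority margin. Mortality of 50 to 52% lies above the 13.6 to 42.8% that the SAP cites, although that range is for attributable mortality, and the 55% composite includes recurrence. This also stands, which is why the 5-point results belong beside them. High mortality is not essential, though: 30 v 20% gives 20%.

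**Consequence.** A reader might infer that a harmful short arm could pass as beneficial. All-cause death is in the primary endpoint (SAP 2.6), deaths and serious events are tabulated (SAP 5.3, 8.3), and the DSMB sees interim primary results (SAP 4). In a joint simulation, assuming a 55% composite in the long arm and equal recurrence risk among those who do not die, trials that both met non-inferiority and showed a spuriously shorter stay made up about 2% at 50 v 40% and 52 v 40%, and 2 to 3.5% at 5-point gaps. The stronger inference is not supported.

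**Antibiotic days.** A reader might extend the criticism fully to SAP 8.6. The intervention acts directly on antibiotic use, and total exposure is a legitimate stewardship measure. Only reading a total lowered by death as a benefit would be wrong.

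**Section 7.2.** The likely intent is a continuous regression with the covariates listed in SAP section 7. That is plausible, but no such model is named.

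**Conclusion.** The omission holds for hospital stay and ventilation. If death ends the count, as the SAP 2.6 totals imply, unequal mortality biases the comparison toward the arm with more deaths: about 8% false findings of shorter stay at a 5-point gap and about 17 to 28% at 10 to 12 points, against 2.5% by chance. Excluding in-hospital deaths gives about 5 to 8% and gives up the randomised comparison. With equal mortality there is no bias. These sizes rest on assumed stay and death-time distributions; the direction rests on the count ending at death and on deaths occurring early enough to shorten it.

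The section 7.2 cross-reference is wrong for all three durations whatever the mortality. The primary non-inferiority conclusion and the sample size are untouched. This should be corrected because it concerns how secondary results will be read, and because the rule should be fixed before an unblinded analyst has to choose one.

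**What to change.** 1. Align SAP 2.6 with 8.4 and 8.5: one definition per outcome, one starting point (enrolment or randomisation), and a statement of how readmission and reintubation count.
2. Analyse stay and ventilation in one of two ways, chosen in advance, with mortality by arm in the same table:
   - hospital-free and ventilator-free days to day 60, death ranked worst, by a site-stratified rank test or proportional-odds model; or
   - cumulative incidence of discharge and of extubation, with death as a competing event.
3. Keep survivor-only medians as description.
4. Keep total antibiotic days as an exposure measure, reported with mortality and also per day alive.
5. In SAP 8.4 to 8.6, replace the reference to section 7.2 with a named model suited to each scale, using the same covariates.

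No new data are needed: SAP 2.7 and section 3 already cover deaths and the discharge, extubation and antibiotic dates. The cost is an SAP amendment, which needs DSMB approval under SAP section 4, and modest programming. The downside of the death-ranked scale is that it is less intuitive than days of stay and partly re-tests mortality, since all deaths share one rank.

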8.5. Duration of Mechanical Ventilation

Time from randomisation to extubation, and time from original intubation to extubation, will be summarised overall and by treatment group using median (IQR) and compared using Wilcoxon rank sum test. Using this as a continuous outcome variable, the analysis described in section 7.2 will be repeated.

8.6. Total Duration of Antibiotics

Total duration of antibiotics from randomisation to 60 days of follow-up will be summarised overall and by treatment group using median (interquartile range) and compared using Wilcoxon rank sum test. Using this as a continuous outcome variable, the analysis described in section 7.2 will be repeated.

8.7. Acquisition of Multidrug Resistant Infection or Colonisation

Acquisition of multidrug resistant infection or colonisation will be summarised overall and by treatment arm (frequency and percentages). Participants will be categorised as either having or not having acquired multidrug resistant infection or colonisation. Using this as a binary outcome variable, the analysis described in section 7.2 will be repeated.

8.8. Number and types of extrapulmonary infections during hospitalisation

Extrapulmonary infection events in sterile sites are most likely to occur in bloodstream infections. Unless infections from other sterile sites exceed >5 episodes in either arm, only bloodstream infections will be summarised overall and by treatment arm (frequency and percentages). Participants will be categorised as either having or not having experienced bloodstream infections post randomisation. Using this as a binary outcome variable, the analysis described in section 7.2 will be repeated.

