4. OBJECTIVES AND OUTCOME MEASURES

Objectives	Outcome Measures	Timepoint(s) of evaluation of this outcome measure (if applicable)
Primary Objective To demonstrate clinical non-inferiority, followed by superiority, of a shorter antibiotic treatment duration compared to a longer duration in adult patients with VAP	Difference in the proportion of participants with the composite endpoint of death and VAP recurrence rate within 60(± 5) days of enrolment	All outcome measures will be assessed within day 60(± 5) of enrolment
Secondary Objectives To define other clinical benefits of shorter antibiotic treatment duration compared to a longer duration in adult patients with VAP	Ventilator-associated events, duration of mechanical ventilation, duration of hospitalisation, acquisition of multidrug resistant infection or colonisation during the hospitalisation, number of days of exposure to antibiotics during hospitalisation, number and types of extrapulmonary infections during hospitalisation (determined from cultures taken from sterile sites), difference in the proportion of participants with primary outcome in subgroups of patients with VAP caused by Gram-negative non-fermenters and carbapenem-resistant bacilli	All outcome measures will be assessed within day 60(± 5) of enrolment
To study the impact of various antibiotic regimen on the microbial community dynamics and diversity in the respiratory and intestinal tracts in individual patients in order to understand colonisation and transmission of MDROs, identify potentially protective components of the microbiome against MDROs	Characteristics of the microbiota will be determined by comparing alpha and beta diversity metrics between the groups of patients, alterations in the repertoire of antibiotic resistant genes, shifts in microbiota functional and metabolic capacity	Respiratory and stool samples will be collected from the study participants within 24 hours of enrolment, weekly during hospitalisation, and at day 28 (± 5) and 60(± 5) after enrolment

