H_0 : There is no difference in the number of sterile site infections in the short and long treatment strategy groups, i.e. $x_s = x_l$;

H_1 : There is a difference in the number of sterile site infections in the short and long treatment strategy groups, i.e. $x_s \neq x_l$;

where x_s is the number of sterile site infections in the short and x_l is the number of sterile site infections in the long treatment strategy groups.

g) Adverse events, i.e. antibiotic related diarrhoea, allergic reactions

Definition: Number and types of adverse events during 60 days of follow-up, which include antibiotic related diarrhoea, allergic reactions, readmissions

H_0 : There is no difference in the number of adverse events in the short and long treatment strategy groups, i.e. $x^{AE}_s = x^{AE}_l$;

H_1 : There is a difference in the number of adverse events in the short and long treatment strategy groups, i.e. $x^{AE}_s \neq x^{AE}_l$;

where x^{AE}_s is the number of adverse events in the short and x^{AE}_l is the number of adverse events in the long treatment strategy groups.

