7.3. Adjustment of P values for Multiple Testing

There is no multiple testing as only a single primary outcome is considered. All additional analyses are undertaken with an intention to further inform the results from the primary analysis. Therefore significance levels used will be 0.05 and 95% confidence intervals will be reported.

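### SAP 8.8 compares only bloodstream infection (yes/no), so the sterile-site endpoint and hypothesis in SAP 2.6(f) go untested, and other sites may not be reported at all

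*SAP*

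**What the plan says.** Protocol section 4 lists among the secondary outcomes the "number and types of extrapulmonary infections during hospitalisation (determined from cultures taken from sterile sites").

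SAP 2.6(f) makes this concrete: "Number and types of bloodstream, bone and joint, intracranial, intraabdominal infections during 60 days of follow-up". Its null hypothesis concerns a count over all of these sites: "There is no difference in the number of sterile site infections in the short and long treatment strategy groups". SAP 2.6 also states that "All statistical tests for the secondary endpoints are standard two-sided superiority tests", and SAP 7.3 sets the level at 0.05.

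SAP 8.8 gives the analysis in three steps.

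- **Premise:** "Extrapulmonary infection events in sterile sites are most likely to occur in bloodstream infections". No figure supports it.
- **Reporting rule:** "Unless infections from other sterile sites exceed >5 episodes in either arm, only bloodstream infections will be summarised overall and by treatment arm".
- **Compared variable:** "Participants will be categorised as either having or not having experienced bloodstream infections post randomisation". This is then analysed by the methods of SAP 7.2.

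SAP 8.8 does not say whether the limit of 5 applies to each site or to all other sites together. No other SAP section tabulates the remaining sites by site and arm.

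**The concern.** There are two separate problems.

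1. **The analysis does not match the endpoint.** A hypothesis about the number of infections at four groups of sites becomes a yes/no comparison at one of them. A trial that followed SAP 8.8 to the letter would never test the hypothesis in SAP 2.6(f).
2. **Reporting depends on the counts by arm.** Whether bone and joint, intracranial and intraabdominal infections are shown depends on one arm passing a limit. SAP 9.2 says the trial statistician is not blinded, so the rule is applied with the counts by arm in view.

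The protocol places this endpoint under the objective of defining other clinical benefits of shorter treatment. A reader weighing that needs every extrapulmonary infection by arm, whichever arm it favours. Under SAP 8.8 an imbalance outside the bloodstream cannot affect the comparison, and it may not appear in a table either.

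**Working it through.** **Texts side by side**

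| | SAP 2.6(f) | SAP 8.8 |
|---|---|---|
| Sites | Bloodstream, bone and joint, intracranial, intraabdominal | Bloodstream only |
| Quantity | Number of infections | Yes/no per participant |
| Other sites in the comparison | Included | Left out, above or below the limit |
| Other sites in the summary | Number and types | Only if more than 5 episodes in either arm |

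The documents give no event rate, power or sample size for this endpoint, so there is no planned figure to reproduce. The calculations below use 230 per arm (SAP 2.2), two-sided tests (SAP 2.6) and 0.05 (SAP 7.3). All event counts and rates are assumptions.

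**1. What can go unreported.** If the limit is pooled over sites, up to 5 episodes in each arm, 10 in total. With one episode per participant, 5/230 = 2.2% of an arm. If the limit applies to each of the three other named groups, the ceiling is 3 × 5 = 15 per arm (15/230 = 6.5%).

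**2. The most uneven split the pooled rule can hide, 5 v 0.** The two-sided Fisher p is 2 × C(230,5)/C(460,5) = 0.061.

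**3. How far chance decides reporting.** Assume equal true rates r in both arms, pooled sites and at most one episode per participant. For one arm, q = P(Binomial(230, r) ≥ 6). For either arm, the probability is 1 − (1 − q)².

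| r | q | Either arm exceeds 5 |
|---|---|---|
| 1% | 0.029 | 5.8% |
| 1.5% | 0.134 | 25% |
| 2% | 0.314 | 53% |
| 2.5% | 0.515 | 76% |
| 3% | 0.690 | 90% |
| 4% | 0.901 | 99% |

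At rates of roughly 1.5% to 2.5%, chance largely settles whether these infections are shown.

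**4. Effect on the comparison, by example.** The pooled z test uses z = (a − b)/230 ÷ √(2p(1 − p)/230), with p = (a + b)/460.

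| Participants with an event | What is counted | z | p |
|---|---|---|---|
| 30 v 20 | Bloodstream only | 1.50 | 0.134 |
| 35 v 20 | Plus 5 v 0, all in different participants | 2.16 | 0.031 |
| 34 v 21 | Plus 4 v 1 | 1.87 | 0.062 |
| 33 v 20 | Plus 5 v 0, two of the five already counted | 1.90 | 0.058 |

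The second row is an assumed extreme. The last two rows show how quickly it weakens.

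**5. Effect on the comparison, by rates.** By simulation, with bloodstream rates equal at 10%, other-site rates of 1% v 3% and different participants affected, the bloodstream-only test rejects 5.0% of the time and an all-site test 10.2%. The bloodstream-only test cannot respond to the difference; the all-site test gains only modest power.

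**The case against.** **The rule is pre-specified, and sparse sites cannot be modelled one by one.** Both are true. Pre-specification does not reconcile SAP 8.8 with SAP 2.6(f) or the protocol, and the rule leaves open whether 5 is per site or pooled. Sparseness is a reason to pool sites into one outcome, which keeps the events. It is not a reason to leave them out of a table.

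**Bloodstream infections will dominate.** They may, but SAP 8.8 gives no figure. If so, including the rest changes little and costs nothing.

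**The data are not lost.** This stands. SAP 2.7 has clinical cultures recorded weekly, and SAP 3 applies a full entry check to microbiological cultures. Endpoint 2.6(d) also picks up multidrug-resistant growth from any source, so resistant isolates from other sites enter SAP 8.7. That cover is partial, because susceptible infections are not captured there. The fault lies in analysis and reporting, not in collection.

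**Stronger readings that the documents do not support.** A reader might infer that the tested outcome is chosen after looking at counts by arm. SAP 8.8 does not say that: the limit governs the descriptive summary, and the compared variable is bloodstream infection throughout. Even if a switch to all sites at the limit were assumed, simulated two-sided type I error is about 0.051–0.054, against 0.048–0.051 without a switch (bloodstream rates 5–15%, other sites 1.5–3%). A reader might also infer that the omission can reverse the endpoint. The example does not show this: 30 v 20 and 35 v 20 point the same way, and only the side of 0.05 changes. Nor do the documents name deep infection as a harm of shorter treatment; the risks the protocol names are recurrence and mortality.

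**Conclusion.** The concern holds in two parts. First, SAP 8.8 does not analyse the endpoint or test the hypothesis set in SAP 2.6(f). Three of four site groups are outside the formal comparison at any count, and a count has become a yes/no variable. This part rests on the text alone.

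Second, whether the other sites are reported depends on counts by arm, so a 5 v 0 split could go unshown. The 2.2% v 0% and p = 0.061 assume that the limit is pooled over sites and that each episode is in a different participant. The shift from p = 0.134 to 0.031 is an illustration at the extreme and should not be cited as an expected effect.

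The reach is limited to one of the seven secondary endpoints in SAP 2.1. The primary outcome, the non-inferiority conclusion and the sample size are untouched. It should be corrected because the plan contradicts itself and can leave reporting incomplete.

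**What to change.** In SAP 8.8:

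- delete the condition of more than 5 episodes;
- define the binary outcome as any sterile-site infection after randomisation, covering every site group in SAP 2.6(f), with bloodstream infection reported as a component;
- tabulate episodes and participants for every site by arm, whatever the count.

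In SAP 2.6(f), restate the hypothesis as a difference in the proportion of participants with such an infection, or keep it as a number and add a count comparison to SAP 8.8.

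Narrowing SAP 2.6(f) to bloodstream infection would also make the two SAP sections agree. It would depart from the protocol's endpoint, and the full table by site would still be needed. If sparse sites must be merged for display, base the rule on totals over both arms.

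The cost is SAP wording and one table. The cultures are already collected.
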